9.5.3 Extrapyramidal Signs

The occurrence of neurological side effects will be assessed by looking at the changes in scores from Baseline to each of the post-Baseline visit for each of the Simpson-Angus scale, Barnes Akathisia scale, and AIMS. For each item on each of these scales, the number (and percentage) of subjects with a worse score at any post-Baseline visit, compared to Baseline, will be presented. A listing of these subjects will also be provided.

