SPN-810 ER formulation exhibited a satisfactory safety and tolerability profile, with low incidence of AEs and no unexpected, life threatening or dose-limiting safety issues. The adverse events (AEs) reported in this study were consistent with the types of events that could be expected in a pediatric population taking low-dose antipsychotic medication and psychostimulant ADHD medication. The overall frequency of events was relatively low, as were discontinuations due to AEs. The frequency of AEs associated with extrapyramidal symptoms (EPS) was also low and the two serious adverse events that occurred were not drug-related.

Other study results further supported a beneficial treatment effect on IA behaviors. The CGI results (Severity and Improvement) were consistent with the findings for the R-MOAS; notable improvement occurred primarily in the Low dose and Medium dose groups. Scores for Swanson, Nolan and Pelham Questionnaire (SNAP-IV) Hyperactivity and Impulsivity did not exhibit statistically significant differences across groups. Numeral trends in SNAP-IV Oppositional Defiant Disorder (ODD) scores, while not always significant, consistently favored the Low dose and Medium dose groups over Placebo.

Study 810P203 was a multicenter open label extension (OLE) to the Phase 2b trial in a pediatric population of subjects 6-12 years of age diagnosed with ADHD and IA (Study 810P203, 2013). The starting dose for this open-label extension study was based on subjects' weight at the end of 810P202. Subjects were initiated at doses of 18 and 36 mg/day, in children weighing less than 30 kg, and more than 30 kg, respectively. The dose was gradually adjusted based on tolerability or effectiveness, regardless of weight group to 9 mg/day, 18 mg/day, 27 mg/day or 36 mg/day. Of the 121 subjects randomized into the double blind Study 810P202, 78 subjects continued on to the OLE study and received SPN-810 for up to 6 months.

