At the end of the Maintenance period, all subjects who complete the study will have the option to participate in an OLE study (Study Protocol 810P304) in which all subjects will receive active SM treatment. Subjects choosing to participate will receive a blinded double-dummy conversion medication card which will adjust the subject's TDD to 36 mg for initiation into the open label extension study (Figure 1). Those subjects who do not elect to participate in this extension will be tapered down prior to discontinuation of SM (Figure 2).

A subject who discontinues early in the Maintenance period, i.e., prior to Visit 7 may be allowed to participate in the OLE on a case-by-case basis after consultation between the Investigator, Medical Monitor, and the Sponsor.

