4.3.2 Treatment Phase: (2-5 weeks)

4.3.2.1 Titration period (2 weeks), Day 1 to Day 14

Inclusion/exclusion criteria will be re-assessed to verify eligibility prior to study randomization at the end of Visit 3. Eligible subjects will be randomized at Visit 3 (Day 1) in a 1: 1 ratio to receive 36 mg/day SPN-810 or placebo and proceed to the two-week Titration period in order to reach the maintenance dose of 36 mg/day over a period of 2 weeks.

4.3.2.2 Flexible Maintenance period (3 weeks), Day 15 to Day 35

Following dose titration, all subjects will remain at the reached dose of SPN-810 (36 mg/day) or placebo on the first week of the Maintenance period. After the first week, the Investigator will clinically assess whether to increase the dose to 45 mg/day SPN-810 or placebo, or remain at 36 mg/day of SPN-810 or placebo. On the following week, the Investigator will re-assess the dosage: the subject may remain at 36 mg/day or 45 mg/day or matching placebo (depending on the dosage from the previous week) or titrate up to the higher dose of 45 mg/day or 54 mg/day of SPN-810 or placebo, respectively. Dose reduction will also be allowed during the second week of the Maintenance period in consultation with the Medical Monitor and the Sponsor; at Visit 6 the Investigator may adjust the dose based upon tolerability.

4.3.3 Conversion Phase (10 days), Day 36 to day 45

At the end of the 3-week Maintenance period (Visit 7), subjects will enter a 10 day Conversion Phase if the subject chooses to enroll into an ongoing open-label extension (OLE) study (i.e., 810P304). A blinded double-dummy conversion card will be distributed to down or up-titrate

This document is confidential. It contains proprietary information of Supernus[®] Pharmaceuticals, Inc. Any viewing or disclosure of such information that is not authorized in writing by the Sponsor is strictly prohibited. Such information may be used solely for the purpose of reviewing or performing this study.

CONFIDENTIAL Version 3

the study medication and matching placebo. Subjects will return to the study site for a final end-of-study (EOS) visit, (Visit 8), after completing the Conversion Phase (Figure 1).

4.3.4 Taper Phase (10 days), Day 36 to day 45

At Visit 7, subjects who opt to discontinue from the study will receive a blinded taper card to titrate down the study medication. At the completion of the Taper Phase, subjects will return to the study site to complete the EOS procedures (Figure 2).

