- 8. Collect blood samples for hematology and chemistry
- 9. Administer Columbia Suicide Severity Rating Scale (C-SSRS)
- 10. Administer Caregiver and Investigator-completed CGI-S scale
- 11. Administer Caregiver and Investigator-completed CGI-I scale
- 12. Administer SNAP-IV, CHQ-PF 28 and SIPA scales
- 13. Administer safety scales (Simpson-Angus, Barnes-Akathisia, AIMS)
- 14. Record adverse events
- 15. Record Infrequent IA Behaviors
- 16. Record concomitant medications
- 17. Collect returned SM; assess treatment compliance
- 18. Dispense SM (either taper or conversion card based upon the subject's decision about participation in the open-label extension)

5.3.8 Visit 8/ End of the Study, Day 46

Visit 8 will occur 10 days (±1 day) following Visit 7 according to the Schedule of Visits and Procedures. These procedures will be performed for all subjects who complete the Maintenance period and for those who discontinue early. Subjects who discontinue after Visit 4 will be offered a taper kit and return to the study site to complete Visit 8. Any subject, who discontinues between Visit 3 and Visit 4, will be instructed to return to the study site for the final visit, within one week after discontinuation.

- 1. Administer R-MOAS scale
- 2. Record vital signs (HR, BP, temperature, and RR)
- 3. Record height, weight and BMI
- 4. Collect blood for hematology and chemistry
- 5. Collect urine for urinalysis, drug screen and pregnancy test
- 6. Administer Columbia Suicide Severity Rating Scale (C-SSRS)
- 7. Administer safety scales (Simpson-Angus, Barnes-Akathisia, AIMS)

- 8. Record adverse events
- 9. Record concomitant medications
- 10. Collect SM and assess treatment compliance
- 11. Collect Diary
- 12. Complete/Discontinue subject

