6.4.4 Assessment of Neurological Side Effects and EPS

6.4.4.1 Simpson-Angus Scale

The Simpson-Angus scale is a 10-item rating scale that is widely used for assessment of neuroleptic-induced Parkinsonism (Simpson 1970). It consists of 1 item measuring gait, 6 items measuring rigidity, and three items measuring glabella tap, tremor and salivation, respectively. This assessment will be administered at Visit 3 and all subsequent visits.

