9.5 Safety Analysis

Evaluation of safety will be performed for the safety population. Safety data that will be evaluated include concomitant medications, AEs, clinical laboratory results, vital signs, ECGs, and findings from the physical examinations. The occurrence of neurological side effects will be assessed by looking at any worsening in scores from Visit 3 to each subsequent visit for each of the Simpson-Angus scale, Barnes Akathisia scale, and AIMS. Suicidal ideation and suicidal behavior will be measured by C-SSRS.

All summary tables related to safety analyses will use the safety population.

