# **7.6** Extrapyramidal Symptoms

Extrapyramidal Symptoms collected using Simpson-Angus Scale, Barnes Akathisia Scale, and Abnormal Involuntary Movement Scale will be summarized and listed by treatment group.

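### The any-visit EPS-scale count in Protocol 9.5.3 has no cut-off before Visit 8, so worsening after conversion to SPN-810 can be counted under placebo

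*Protocol*

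**What the plan says.** **Counting rule.** Protocol 9.5.3 plans two things for the three scales: changes in score from baseline to each later visit, and an item-by-item count in which "the number (and percentage) of subjects with a worse score at any post-Baseline visit, compared to Baseline, will be presented", with a listing of those subjects. Protocol 9.5 describes the same assessment as "any worsening in scores from Visit 3 to each subsequent visit". Neither section names a last eligible visit.

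**When the scales are given.** Protocol 6.4.4.1 says of the Simpson-Angus scale: "This assessment will be administered at Visit 3 and all subsequent visits". Sections 6.4.4.2 and 6.4.4.3 say the same for Barnes and AIMS. Table 1 and the procedure list in 5.3.8 include all three at Visit 8 (Day 46).

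**What happens before Visit 8.** Under Protocol 4.3.3, after Visit 7 "subjects will enter a 10 day Conversion Phase if the subject chooses to enroll into an ongoing open-label extension (OLE) study". Section 4.2 says that subjects choosing the extension "will receive a blinded double-dummy conversion medication card which will adjust" the total daily dose to 36 mg. The synopsis describes the card as moving doses down or up so that subjects enter the extension on 36 mg/day SPN-810. No exception is made for the placebo arm.

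**Arm label.** Protocol 8.3 bases the analysis populations on randomized treatment. Nothing relabels a subject at conversion.

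**SAP.** Section 7.6 says only that the scores from the Simpson-Angus Scale, Barnes Akathisia Scale and "Abnormal Involuntary Movement Scale will be summarized and listed by treatment group". It gives no visit window and does not mention the any-visit count.

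**The concern.** An any-visit count compares the arms cleanly only while each subject is on the randomized treatment. For placebo subjects who enter the extension, the last rating in the window follows active dosing. If such a subject first worsens then, the count records it against placebo. In the placebo arm this error can only raise the count, so it tends to narrow the apparent EPS difference.

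Safety is part of the primary objective (Protocol 3.1, SAP 2), and EPS assessed by these scales is a named safety endpoint in the protocol synopsis. A between-arm count of scale worsening should therefore not mix the two treatments.

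**Working it through.** The plan states no figure for this point, so the check is to trace the visit window, then illustrate the size.

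**Tracing the window**

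1. Visit 7 is Day 36, conversion runs from Day 36 to Day 45, and Visit 8 is Day 46. A Visit 8 rating in an extension subject therefore follows the conversion card.
2. The planned active maintenance doses are 36, 45 or 54 mg/day. Moving up to 36 mg/day therefore describes mainly placebo subjects.
3. Visit 8 is a post-baseline visit, so 9.5.3 includes it, and the subject is still shown as placebo.
4. Other windows stop earlier. The synopsis sends AEs with onset after Visit 7 in extension subjects to the extension study. Protocol 9.5.1 splits the TEAE tables into Titration, Maintenance and the two combined. The exposure categories in SAP 5.6 end at Week 5. None of these limits applies to scale scores.
5. SAP 7.2 and 7.3 summarize laboratory tests and vital signs to EOS, which is Visit 8 in Table 1. The SAP therefore does not treat data after Visit 7 as out of scope in general.

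**Illustration of size**

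For one scale item, let
- p0 = proportion of placebo subjects worse at some visit up to Visit 7 (assumed);
- f = share of the placebo arm that converts;
- q = proportion of converters not worse before who become worse at Visit 8 (assumed).

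The any-visit placebo rate is p0 + (1 − p0) × f × q. The extra placebo subjects number 93 × (1 − p0) × f × q, where 93 is the planned arm size (Protocol 5.1).

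For f, the only extension share in the documents is from the phase 2b study in ages 6 to 12 (Protocol 2.4). Of 121 randomized subjects, "78 subjects continued on to the OLE study and received SPN-810 for up to 6 months". So f = 78/121 = 0.645, and 0.645 × 93 is about 60 placebo subjects. With p0 = 5%:

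| q | Any-visit placebo rate | Subjects of 93 | Extra over the Visit 7 cut-off (4.7 of 93) |
|---|---|---|---|
| 5% | 0.05 + 0.95 × 0.645 × 0.05 = 8.1% | 7.5 | 2.8 |
| 10% | 0.05 + 0.95 × 0.645 × 0.10 = 11.1% | 10.3 | 5.7 |
| 20% | 0.05 + 0.95 × 0.645 × 0.20 = 17.2% | 16.0 | 11.4 |

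Over f = 0.40 to 0.80, p0 = 5% to 10% and q = 5% to 20%, the extremes are:
- lowest: 93 × 0.90 × 0.40 × 0.05 = 1.7;
- highest: 93 × 0.95 × 0.80 × 0.20 = 14.1.

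The upper value f = 0.80 corresponds to every completer converting at the planned dropout of about 20% (Protocol 9.3).

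**The case against.** Several objections have force and limit the point.

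- **Visit 8 can be recovered.** A reader might infer that the crossover visit is lost in the reporting. It is not. Section 9.5.3 also plans changes at each visit and a listing of subjects who worsen, and SAP 5.1 promises listings of all data. Only the any-visit count mixes the treatments.
- **The SAP has precedence.** Protocol 8.1 says the SAP supersedes the protocol's methods, and SAP 7.6 does not repeat the any-visit rule. It is therefore not settled that the count will be produced. But 7.6 neither excludes Visit 8 nor supplies another rule, so a programmer must fall back on 9.5.3 or improvise.
- **The main clinical EPS evidence lies elsewhere.** A reader might infer that the whole trial understates EPS risk. The documents do not support that. Events of special interest are reported on their own form, Protocol 6.4.4.4 says a positive scale finding need not be an EPS event, and the protocol's AE reporting is split by period.
- **The loss of contrast is not established.** Suppose rates to Visit 7 were 5% on placebo and 15% on SPN-810. With q = 10%, one could infer a fall in the difference from 10 to about 4 percentage points (15 − 11.1). All these rates are assumed, the extension share is from another study, and the result needs no new SPN-810 cases at Visit 8. Any such cases would offset the narrowing. Nor do 9.5.3 or SAP 7.6 plan a between-arm test.
- **A plain Visits 4 to 7 window would do harm.** Subjects who stop between Visits 3 and 4 have their only scheduled post-baseline rating at the end-of-study visit (Protocol 4.3.6, 5.3.8, 5.7). Subjects who stop later may also be first rated worse there. Dropping those ratings could hide EPS that led to stopping. The fix must keep them.
- **The dosing detail is partly inferred.** The conversion schematic is not available here, so the number of days at each dose is unknown. Placebo subjects who taper are unaffected.

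**Conclusion.** The point holds as a defect of one planned output. Followed as written, the item-level any-visit count in Protocol 9.5.3 includes Visit 8 ratings made after placebo subjects have been converted to SPN-810, counts them under placebo, and so can understate the between-arm difference. SAP 7.6 does not remove the problem.

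The size is unknown. The range of about 2 to 14 extra placebo subjects of 93 is an illustration that rests on assumed rates, an assumed range for the converting share, and the planned arm size. SAP 5.1 says the study was halted, so fewer subjects may be available. The conclusion also rests on reading the conversion text as giving SPN-810 to placebo subjects, which is the natural reading of the synopsis and Protocol 4.2.

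**What to change.** In Protocol 9.5.3 and SAP 7.6, limit the by-arm any-visit count to ratings made before the first dose of conversion medication. In practice this means Visits 4 to 7, plus the end-of-study or early-termination rating of subjects who discontinued early and took no conversion card. For completers the window then ends at Visit 7, whichever card they take.

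Report completers' Visit 8 ratings, and any other rating made after conversion dosing, in a separate table by randomized arm and by what was received after Visit 7 (conversion or taper). This matches the cut-off that the synopsis already applies to AEs of extension subjects.

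The cost is one sentence and one table, with no change to visits, dosing or data collection. The downside is that worsening first seen at Visit 8 in SPN-810 completers moves from the main count to the separate table, so the two should be presented together.

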9.5.4 Laboratory Values

Clinical laboratory values will be summarized by visit and by treatment group using descriptive statistics for hematology and chemistry. For quantitative laboratory parameters, both actual values and change from Baseline values will be summarized.

Laboratory test results will be assigned a low, normal, high (LNH) classification according to whether the values were below (L), within (N), or above (H) the laboratory parameters' reference ranges provided by the central laboratory. Within-treatment comparisons will be based on three by three tables (shift tables) that, for a particular laboratory test, compare the LNH classification at baseline to the LNH classification at visit. By subject-listings of all abnormal laboratory values, i.e., those with L or H classification will be provided.

9.5.5 Vital Signs, Height, Weight and BMI

Vital signs will be summarized by the visit and by treatment group using descriptive statistics. Both actual values and changes from the Baseline to final visit will be summarized. Descriptive summary statistics (mean, SD, median, and range) for vital sign data, height, weight and BMI will be evaluated by treatment group.

9.5.6 ECG Results

Tabular summaries of the quantitative ECG parameters and the overall ECG findings (normal, abnormal not clinically significant, or abnormal clinically significant) will be presented. The QT will be corrected using Fridericia's method.

ECG results will be summarized by visit and by treatment group using descriptive statistics (for quantitative ECG parameters) and frequency tables (for qualitative ECG parameters, including the overall ECG finding). For quantitative ECG parameters, both actual values and change from Baseline values will be summarized.

9.5.7 Physical Examinations

Findings from the physical examinations will be listed for each system or area examined.

9.5.8 Infrequent Behaviors Checklist

Infrequent behaviors will be listed for each subject by treatment group.

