The primary efficacy endpoint is the percent change (PCH_T) in the frequency (unweighted score) of IA behaviors per 7 days in the Treatment Phase (titration + maintenance) relative to the Baseline period calculated over the number of days with non-missing IA diary data.

The primary efficacy endpoint PCH_T will be calculated by $PCH_T = 100^*(T - B)/B$, where T and B are IA behavior frequencies per 7 days during the Treatment Phase and Baseline period, respectively. The IA behavior frequency per 7 days is defined as (SUM/DAY) x 7, where SUM is the total of the 15 IA behaviors reported in IA diary, and DAY is the number of days with non-missing IA score in the IA diary during the specified study period.

Key Secondary Efficacy Endpoints:

- 1. Investigator-rated CGI-S scale
- 2. R-MOAS rating scale
- 3. R-MOAS remission rate defined by a score ≤ 10

Additional Secondary Endpoints:

- 1. Investigator-rated CGI-I scale
- 2. Caregiver-rated CGI-I scale
- 3. Caregiver-rated CGI-S scale
- 4. SNAP-IV rating scale
- 5. CHQ-PF28 rating scale
- 6. SIPA rating scale

Additional Secondary Safety and Tolerability Endpoints:

- 1. Incidence of Adverse Events
- 2. Incidence of Extrapyramidal Symptoms (EPS) as assessed by Simpson-Angus Scale Barnes Akathisia Scale, Abnormal Involuntary Movement Scale
- 3. Columbia Suicide Severity Rating Scale (C-SSRS)
- 4. Laboratory Parameters (Hematology, Chemistry, Urinalysis, Insulin and Prolactin)
- 5. Vital signs, Standardized BMI, Physical Examination and ECG (12-lead)
- 6. Infrequent Behaviors Checklist

Exploratory Endpoints:

1. IA Diary Cross-Validation

The data generated from 810P301 and 810P302 pediatric studies during the diary validation process may be used for cross-validation of the IA Diary in adolescents. If the decision is made to proceed with the analysis, the cross-validation plan and results will be provided in a separate stand-alone report.

This document is confidential. It contains proprietary information of Supernus[®] Pharmaceuticals, Inc. Any viewing or disclosure of such information that is not authorized in writing by the Sponsor is strictly prohibited. Such information may be used solely for the purpose of reviewing or performing this study.

2. Population Pharmacokinetics/Pharmacodynamics:

3. Pharmacogenomics (PGx) Testing:

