3.2 Secondary Objectives

The key secondary objectives of this study are to assess the effect of SPN-810 on the following scales:

- 1. Investigator-rated Clinical Global Impression Severity Scale (CGI-S);
- 2. Retrospective Overt Modified Aggression Scale (R-MOAS);
- 3. Percent of children whose IA behaviors were remitted at the end of the study measured by R-MOAS score \leq 10.

Additional secondary objectives are to assess the effect of treating adolescents with SPN-810 on the following:

- 1. Investigator- rated Clinical Global Impression Improvement Scale (CGI-I);
- 2. Caregiver-rated CGI-I Scale;
- 3. Caregiver-rated Clinical Global Impression Severity Scale (CGI-S);
- 4. Inattention, Hyperactivity-Impulsivity and ODD measured by the SNAP-IV rating scale;
- 5. Child Health Questionnaire Parent Form 28-item (CHQ-PF28);

- 6. Stress Index for Parents of Adolescents (SIPA);
- 7. Safety monitoring.
 - a. Incidence of Adverse Events
 - b. Incidence of Extrapyramidal Symptoms (EPS) as assessed by Simpson-Angus Scale Barnes Akathisia Scale, Abnormal Involuntary Movement Scale
 - c. Columbia Suicide Severity Rating Scale (C-SSRS)
 - d. Laboratory Parameters (Hematology, Chemistry, Urinalysis, Insulin and Prolactin)
 - e. Vital signs, Standardized BMI, Physical Examination and ECG (12-lead)
 - f. Infrequent Behaviors Checklist

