A list of 15 behaviors such as Teasing, Spitting, Biting, Weapons, Ripping, Breaking, Vandalizing, Destroying, Fire Setting, Hitting Animal, Kicking self, Kicking Animal, Severe Injury Self, Severe Injury Others and Severe Injury Animal, were considered infrequent in the qualitative study conducted during the IA diary development (Sponsor Study 810501, 2015). The incidence of these infrequent IA behaviors will be assessed on paper at Visit 2 and using the checklist in the electronic IA diary from Visit 3 to Visit 7.

As an exploratory measure, this study will also permit us to psychometrically cross-validate, if needed, the IA diary as a tool to measure IA behaviors in subjects aged 12 to 17 years with ADHD and comorbid IA.

Additional exploratory analyses include the pharmacokinetic/pharmacodynamics and pharmacogenomics of molindone.

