Each event will be characterized by a checklist of one or more behaviors observed during the day. The checklist will indicate whether each behavior was observed (coded 1) or was not observed (coded 0) during the incidence of an event. Each day can have multiple events. A day can have no event, as can be attested in the evening diary. In this case, if no event is reported during a day, and the evening diary confirms this, the daily event score for that subject will be 0. Behaviors not on this list will not be captured.

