## **3.4** Safety Endpoints

- 1. Incidence of Adverse Events
- 2. Incident of Extrapyramidal Symptoms (EPS)

- 3. Clinical laboratory evaluations
- 4. Vital signs and ECG
- 5. Suicidal symptoms (C-SSRS)
- 6. Infrequent behaviors

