### **5 STATISTICAL METHODS and ANALYSES**

#### **5.1** General Considerations

Because SPN-810 did not show efficacy for the Treatment of Impulsive Aggression in the two previous Double-Blind Studies (810P301 and 810P302), the conduct of this study (810P503) was halted. Therefore, the analysis will be limited to the primary, key secondary endpoints and safety data, which will include adverse events (AEs), Extrapyramidal Symptoms (EPS), Simpson-Angus Scale, Barnes Akathisia Scale, and Abnormal Involuntary Movement Scale, clinical laboratory evaluations, vital signs, suicidal symptoms (C-SSRS) and ECG results.

All descriptive statistical analyses will be performed using SAS (Version 9.4), unless otherwise noted and will be presented by treatment groups (Placebo, SPN-810).

Continuous variable summaries will include the number of subjects (n) with non-missing values, mean, standard deviation (SD), median, interquartile range (Q1 and Q3), minimum, and maximum.

Categorical variable summaries will include the frequency and percentage of subjects who are in the category or each possible value. In general, the denominator for the percentage calculation will be based upon the total number of subjects in the study population for the treatment groups, unless otherwise specified. The denominator for by visit displays will be the number of subjects in the relevant study population with non-missing data at each study visit.

In general, the baseline value for a variable is defined as the last observation prior to the first dose of double-blind study medication, ideally Visit 3, but including the screening value, if necessary.

All data will be presented in Listings.

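### Infrequent behaviors are a named safety endpoint whose incidence is to be assessed, but neither the protocol nor the SAP plans a by-arm count of them, only listings

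*Protocol*

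**What the plan says.** **Status as an endpoint.** The protocol synopsis names "6. Infrequent Behaviors Checklist" under the additional secondary safety and tolerability endpoints. Section 3.2 repeats it under safety monitoring as "f. Infrequent Behaviors Checklist". SAP 3.4 keeps it as the sixth and last safety endpoint: "Infrequent behaviors".

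**What is measured, and when.** Protocol 4.1 states: "The incidence of these infrequent IA behaviors will be assessed on paper at Visit 2", followed by electronic recording at Visits 3 to 7. Section 6.4.10 gives the 15 behaviors and the recall period: since Screening at Visit 2, and since the previous visit after that.

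**What is done with the data.** The synopsis says that the data are listed, and Protocol 9.5.8 says the same: "Infrequent behaviors will be listed for each subject by treatment group". SAP 5.1 limits the analysis, because the study was halted, to the primary endpoint, the key secondary endpoints and "safety data, which will include adverse events (AEs), Extrapyramidal Symptoms (EPS), Simpson-Angus Scale, Barnes Akathisia Scale, and Abnormal Involuntary Movement Scale", then laboratory evaluations, vital signs, C-SSRS and ECG. The checklist is not in that list. The same section ends by saying that all data will appear in listings.

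**The concern.** An incidence is a number of subjects with the event over a number at risk. A per-subject listing is the raw material for that figure, not the figure itself. The plan names the endpoint and describes the measure, but does not specify the output that would report it.

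This trial aims to reduce aggression, so the content matters. The primary variable is an unweighted count of 15 other behaviors, and for that score Protocol 6.1.1 says "Behaviors not on this list will not be captured". The diary frequency could fall because arguing and yelling become less common while some checklist behaviors move the other way. No planned table of the checklist behaviors would let a reader compare the arms on that point.

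**Working it through.** The plan gives no figure to reproduce, and the point needs no sample-size arithmetic. The check is to match each endpoint to an analysis, then ask whether another output fills the gap.

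**1. SAP 3.4 endpoints against SAP Section 7.**

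| SAP 3.4 safety endpoint | Named in SAP 5.1 scope | Summary in SAP Section 7 |
|---|---|---|
| 1. Adverse events | yes | 7.1 |
| 2. Extrapyramidal symptoms | yes | 7.6, and 7.1.5 for events of special interest |
| 3. Clinical laboratory | yes | 7.2 |
| 4. Vital signs and ECG | yes | 7.3 and 7.4 |
| 5. C-SSRS | yes | 7.5, number and percent by arm |
| 6. Infrequent behaviors | no | none |

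Five of the six endpoints have a matching summary and one does not.

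**2. Protocol wording against protocol analysis.** Section 4.1 speaks of incidence. The synopsis and Section 9.5.8 plan a listing. The listing-only plan is therefore in the protocol itself and does not come from the reduced analysis that SAP 5.1 ties to the halt.

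**3. Which plan governs.** Protocol 8.1 says that the SAP supersedes the protocol's analysis methods. What remains in force for the checklist is the general listing statement in SAP 5.1. That statement does not mention the checklist, or the arrangement by treatment group that Protocol 9.5.8 asked for.

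**4. Whether another by-arm output supplies the count.**
- *IA diary score.* It covers the other 15 behaviors only.
- *R-MOAS.* The form in Appendix 12.1 has items that overlap with the checklist. One combines setting a fire with throwing things at people, and others cover damaging property and severe self-injury. SAP 6.2 summarizes the score and the remission rate, not the items.
- *C-SSRS.* SAP 7.5 counts attempts and suicidal behavior by arm. It does not cover harm to other people, animals or property.
- *Adverse events.* An injury recorded as an adverse event enters the tables in SAP 7.1. Under the definition in Protocol 6.4.2, using a weapon or hurting another person or an animal need not be an adverse event of the subject.

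These outputs overlap with parts of the checklist, but none counts the checklist behaviors.

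**5. Whether the data support a table.** Table 1 schedules the checklist at Visits 2 to 7 and not at Visit 8.
- *Visit 3.* The checklist is recorded at the visit where study medication is first dispensed, and it looks back to Visit 2. It is a usable pre-treatment reference.
- *Visit 2.* It looks back to Screening, and Table 1 footnote e allows Visits 1 and 2 on the same day. The recall period can then be empty.
- *Visits 4 to 7 (Days 15, 22, 29 and 36).* They look back 15 − 1 = 14, then 22 − 15 = 7, 29 − 22 = 7 and 36 − 29 = 7 days, a total of 14 + 7 + 7 + 7 = 35 days. The Visit 3 recall runs over a baseline that Section 4.3.1.2 allows to last 15 to 30 days. The two percentages cover different lengths of time, so they should not be subtracted to give a change. The comparison between arms at Visits 4 to 7 is not affected by this mismatch.
- *Early discontinuation.* Protocol 5.3.8 brings these subjects back for Visit 8, where no checklist is scheduled. A subject who stops before Visit 4 may have no post-baseline checklist, so the denominator has to be stated.

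**The case against.** The case on the other side has several sound parts.

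- **The data are not lost.** SAP 3.4 keeps the endpoint, and the listing statement in SAP 5.1 still outputs the records. A reader might infer that the SAP discards the checklist, but the documents do not support that. What is missing is a summary.
- **The SAP 5.1 list is weak evidence of exclusion taken alone.** SAP 6.3 goes on to summarize CGI-I, SNAP-IV, CHQ-PF28 and SIPA, which lie outside the stated scope. The point therefore rests on the absence from 5.1 together with the absence of any entry in 7.1 to 7.6.
- **The study was halted and the SAP is descriptive throughout.** This gives a reason for fewer outputs and lowers the practical weight. It does not account for the gap, because safety data stay in scope and the protocol planned only a listing before the halt.
- **Severe aggression is not invisible by arm.** R-MOAS, C-SSRS and the adverse event tables would show part of it. A reader might infer that nothing in the reported tables could reveal a rise, and that is too strong. Nor is the whole checklist severe: teasing and spitting are on it.
- **A listing can be counted by hand, and physical examination findings are also only listed.** That is true, but the protocol does not describe physical examination findings as an incidence.
- **The sentence in Protocol 6.1.1 about behaviors that are not captured concerns the diary score only.** The checklist is collected separately. It shows what the primary endpoint leaves out, not that the data are missing.

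**Conclusion.** The point holds as a mismatch between a named safety endpoint and its analysis. One of the six SAP 3.4 safety endpoints has no summary, and the plan as written gives no by-arm number or percentage for any of its 15 behaviors. Some of these are serious and some mild, and related instruments capture part of the same ground indirectly.

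No precision is attached. A reader might compute a confidence interval from the planned 93 subjects per arm, but the study was halted, the documents give no achieved number, and they give no expected incidence for these behaviors. There is also no information in the documents that severe behaviors rise on drug. The claim is only that the planned tables would not report them.

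The conclusion assumes that the SAP governs, as Protocol 8.1 says, and that no table outside the SAP text was intended. In a halted, descriptive study the weight is moderate, but the correction is nearly free and should be made.

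**What to change.** Add a Section 7.7 to the SAP for the Infrequent Behaviors Checklist:

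- By arm, n (%) of subjects with any infrequent behavior, and with each of the 15 behaviors, recorded at Visits 4 to 7.
- Denominator: subjects with at least one post-baseline checklist, with that number shown for each arm.
- The Visit 3 checklist shown alongside as the pre-treatment reference, with a note that its recall period differs in length from Visits 4 to 7.
- Visit 2 data in a listing only.

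Add infrequent behaviors to the safety data named in SAP 5.1, so that Sections 3.4, 5.1 and 7 agree.

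The cost is one additional descriptive table. The data are already collected at scheduled visits, and no test or new assessment is needed.
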